### **ABT-333**

An ABT-333 dose of 250 mg BID using the optimized tablet formulation that is expected to provide exposures comparable to the 400 mg BID dose used in Phase 2 studies has been selected to for Phase 3 studies. The same dose and formulation was used in western Phase 3 studies. This is based on comparable efficacy and better safety profile compared

to exposures at higher ABT-333 doses. Comparable viral load decline following monotherapy (approximately 1 log10 IU/mL) was observed at exposures greater than that achieved with the 400 mg BID dose evaluated in western Phase 2 studies. Additionally, the 400 and 800 mg BID doses resulted in identical SVR rates (63%) when combined with pegIFN and RBV for 12 weeks followed by 36 weeks of pegIFN + RBV, indicating that increasing ABT-333 dose > 400 mg BID did not improve efficacy. Furthermore, available data from the Phase 2b study indicates that when ABT-333 400 mg BID dose is combined with ABT-450, ABT-267 and RBV for 12 weeks, very high SVR12 rates were observed in treatment-naïve and treatment-experienced subjects (> 90%). While both the 400 mg BID and 800 mg BID doses of ABT-333 in combination with pegIFN and RBV were well tolerated by HCV-infected subjects for 12 weeks, the 800 mg BID dose was associated with a greater mean hemoglobin reduction compared to the 400 mg BID dose and compared to placebo plus pegIFN and RBV. Therefore, 400 mg ABT-333 in tablet formulation is favored.

In the western subjects, the 250 mg optimized tablet used in the current study has comparable bioavailability to the 400 mg tablet formulation used in western Phase 2 studies. Hence, the ABT-333 250 mg optimized tablet dosed BID was selected as the Phase 3 formulation as it provides exposures that maximizes efficacy and a superior safety profile compared to higher ABT-333 doses.

The ABT-333 250 mg optimized tablet, alone or in combination, has not been evaluated in Chinese subjects. However, ABT-333 400 mg tablet (which is bioequivalent to the ABT-333 250 mg optimized tablet) was evaluated as a part of the 3-DAA regimen, ABT-450/r + AB-267 + ABT-333, in Chinese and Western subjects (Study M12-221). Following administration of the 3-DAA combination (ABT-450/r 150/100 mg QD + ABT-267 25 mg QD + ABT-333 400 mg BID) for 21 day, ABT-333 exposures in Chinese subjects were comparable to Caucasian subjects with this 400mg tablet formulation. Thus, same dose of ABT-333, 250 mg optimized tablet, can be used in Chinese and Western subjects.

### **ABT-267**

An ABT-267 dose of 25 mg QD using the ABT-450/r/ABT-267 co-formulated tablet has been selected to for Phase 3 studies. The same dose and formulation was used in Western Phase 3 studies.

Compared to higher doses, the 25 mg QD dose provided comparable viral load decline following monotherapy and lower potential to decrease ABT-450 exposures. In Western subjects, following 2 to 3 days of ABT-267 monotherapy at doses of 1.5 mg to 200 mg QD, the 25 mg dose of ABT-267 showed viral load decline comparable to higher doses with none of the rebound between doses seen at lower doses. Resistance analysis following monotherapy suggests that doses significantly greater than 25 mg would be needed to improve the resistance profile as a variety of NS5A resistant mutants were observed following monotherapy with doses of 5 mg to 200 mg. In addition, higher ABT-267 doses have been associated with decreases in ABT-450 exposures; the ABT-267 200 mg dose resulted in ~80% lower ABT-450 exposures when ABT-450 250 mg was dosed with 100 mg ritonavir. Hence, doses > 25 mg could decrease the exposures of the "anchor" molecule ABT-450, without providing significant benefit in terms of improved efficacy. Additionally, available data from the Phase 2b study indicates that when ABT-267 25 mg QD dose is combined with ABT-450, ABT-333 and RBV for 12 weeks, very high SVR12 rates were observed in treatment-naïve and treatment experienced subjects (> 90%).

In Western subjects, the co-formulated ABT-450/r/ABT-267 formulation used in the current study has ABT-267 bioavailability comparable to the ABT-267 25 mg tablet used in Phase 2 studies. In addition, ABT-450 exposures from the ABT-450/r/ABT-267 co-formulated tablets are comparable between Chinese and Western subjects. Thus, same dose of ABT-450 can be used in Chinese and Western subjects.

Hence, the ABT-267 dose in the current study is the 25 mg dose, as it provides exposures that maximizes efficacy without compromising ABT-450 exposures.

## **RBV**

The daily dose of RBV selected in Western Phase 2 and 3 studies is 1000 mg to 1200 mg, divided twice daily, and based on subject weight. This dose was chosen as it was the approved dose for treatment of adult patients with chronic hepatitis C infection in combination with pegIFN. The same dose is selected for this study because its safety profile has been well characterized when administered with pegIFN, including the incidence of hemolytic anemia, and there are well-defined dose reduction criteria in the event of RBV-induced anemia. In addition, this dose was studied in the absence of pegIFN in subjects with chronic hepatitis C infection in Studies M12-267, M12-746, M12-998 and M11-652 and was found to be generally safe and well-tolerated and resulted in high SVR rates.

In Chinese subjects, the recommended dose of RBV with an IFN-based regimen is weight based, 1000 mg daily in subjects with a body weight of less than 75 kg, and 1200 mg daily in subjects with a body weight of greater than or equal to 75 kg, per the Chinese HCV Treatment Guidelines. Hence, for the Regional Phase 3 studies, the proposed RBV dose is weight-based 1000 mg or 1200 mg.

Doses comparable to, and higher than, the DAA doses to be administered in this study have been studied in single- and multiple-dose healthy volunteer studies and administered to western HCV-infected subjects as monotherapy or in combination with pegIFN/RBV and found to be generally safe and well tolerated. In addition, the pharmacokinetics of ABT-450, ABT-267 and ritonavir when given in combination to western subjects with mild hepatic impairment were comparable to or slightly lower than in subjects with normal hepatic function. The area under the concentration curve (AUC) of ABT-450 and ABT-267 were comparable ( $\leq 30\%$  change) in subjects with mild hepatic impairment compared to healthy controls. The AUC for ritonavir was 34% lower in subjects with mild hepatic impairment. Additionally, based on the package insert for RBV, dose adjustments are not required in subjects with mild hepatic impairment.

Based on these data, no dose adjustment is required for Chinese subjects with compensated cirrhosis taking the DAA combination in this study. The doses of ABT-267, ABT-333 and ABT-450/r chosen for this study in compensated cirrhotic subjects are the same that was used in Phase 3 studies for the IFN-free 3-DAA Study in Western subjects (Study M13-099).

The maximum dose of ABT-450/r/ABT-267 75 mg/50 mg/12.5 mg tablets will not exceed 150 mg/100 mg/25 mg per day for 12 weeks. The maximum dose of ABT-333 250 mg tablets administered in this study will not exceed 500 mg per day for 12 weeks. The maximum RBV dose administered in this study will not exceed 1200 mg, divided twice daily for 12 weeks.

## **6.0 Adverse Events**

The investigator will monitor each subject for clinical and laboratory evidence of adverse events on a routine basis throughout the study. The investigator will assess and record any adverse event in detail including the date of onset, event diagnosis (if known) or sign/symptom, severity, time course (end date, ongoing, intermittent), relationship of the adverse event to study drug, and any action(s) taken. For serious adverse events considered as having "no reasonable possibility" of being associated with study drug, the investigator will provide an Other cause of the event. For adverse events to be considered intermittent, the events must be of similar nature and severity. Adverse events, whether in response to a query, observed by site personnel, or reported spontaneously by the subject will be recorded.

All adverse events will be followed to a satisfactory conclusion.

### **6.1 Definitions**

#### **6.1.1 Adverse Event**

An adverse event (AE) is defined as any untoward medical occurrence in a patient or clinical investigation subject administered a pharmaceutical product and which does not

necessarily have a causal relationship with this treatment. An adverse event can therefore be any unfavorable and unintended sign (including an abnormal laboratory finding), symptom, or disease temporally associated with the use of a medicinal (investigational) product, whether or not the event is considered causally related to the use of the product.

Such an event can result from use of the drug as stipulated in the protocol or labeling, as well as from accidental or intentional overdose, drug abuse, or drug withdrawal. Any worsening of a pre-existing condition or illness is considered an adverse event.

Worsening in severity of a reported adverse event should be reported as a new adverse event. Laboratory abnormalities and changes in vital signs are considered to be adverse events only if they result in discontinuation from the study, necessitate therapeutic medical intervention, meets protocol specific criteria (see Section 6.7 regarding toxicity management) and/or if the investigator considers them to be adverse events.

An elective surgery/procedure scheduled to occur during a study will not be considered an adverse event if the surgery/procedure is being performed for a pre-existing condition and the surgery/procedure has been pre planned prior to study entry. However, if the pre-existing condition deteriorates unexpectedly during the study (e.g., surgery performed earlier than planned), then the deterioration of the condition for which the elective surgery/procedure is being done will be considered an adverse event.

### **6.1.2 Serious Adverse Events**

If an adverse event meets any of the following criteria, it is to be reported to AbbVie as a serious adverse event (SAE) within 24 hours of the site being made aware of the serious adverse event.

Death of Subject	An event that results in the death of a subject.
Life-Threatening	An event that, in the opinion of the investigator, would have resulted in immediate fatality if medical intervention had not been taken. This does not include an event that would have been fatal if it had occurred in a more severe form.

Hospitalization or Prolongation of Hospitalization	An event that results in an admission to the hospital for any length of time or prolongs the subject's hospital stay. This does not include an emergency room visit or admission to an outpatient facility.
Congenital Anomaly	An anomaly detected at or after birth, or any anomaly that results in fetal loss.
Persistent or Significant Disability/Incapacity	An event that results in a condition that substantially interferes with the activities of daily living of a study subject. Disability is not intended to include experiences of relatively minor medical significance such as headache, nausea, vomiting, diarrhea, influenza, and accidental trauma (e.g., sprained ankle).
Important Medical Event Requiring Medical or Surgical Intervention to Prevent Serious Outcome	An important medical event that may not be immediately life-threatening or result in death or hospitalization, but based on medical judgment may jeopardize the subject and may require medical or surgical intervention to prevent any of the outcomes listed above (i.e., death of subject, life threatening, hospitalization, prolongation of hospitalization, congenital anomaly, or persistent or significant disability/incapacity). Additionally, any elective or spontaneous abortion or stillbirth is considered an important medical event. Examples of such events include allergic bronchospasm requiring intensive treatment in an emergency room or at home, blood dyscrasias or convulsions that do not result in inpatient hospitalization, or the development of drug dependency or drug abuse.

For serious adverse events with the outcome of death, the date and cause of death will be recorded on the appropriate case report form.

## **6.2 Adverse Event Severity**

The investigator will use the following definitions to rate the severity of each adverse event:

Mild	The adverse event is transient and easily tolerated by the subject.
Moderate	The adverse event causes the subject discomfort and interrupts the subject's usual activities.
Severe	The adverse event causes considerable interference with the subject's usual activities and may be incapacitating or life-threatening.

### 6.3 Relationship to Study Drug

The investigator will use the following definitions to assess the relationship of the adverse event to the use of DAAs (ABT-450/r/ABT-267 and ABT-333), and RBV:

Reasonable Possibility	An adverse event where there is evidence to suggest a causal relationship between the study drug and the adverse event.
No Reasonable Possibility	An adverse event where there is no evidence to suggest a causal relationship between the study drug and the adverse event.

For causality assessments, events assessed as having a reasonable possibility of being related to the study drug will be considered "associated." Events assessed as having no reasonable possibility of being related to study drug will be considered "not associated." In addition, when the investigator has not reported a causality or deemed it not assessable, AbbVie will consider the event associated.

If an investigator's opinion of no reasonable possibility of being related to study drug is given, another cause of the event must be provided by the investigator for the serious adverse event.

[figure not shown]
### 6.4 Adverse Event Collection Period

All serious adverse events as well as protocol-related nonserious adverse events will be collected from the time the subject signed the study-specific informed consent until study drug administration. From the time of study drug administration until 30 days after last administration AEs and SAEs will be collected whether solicited or spontaneously

reported by the subject. From 30 days after last dose until the end of study, SAEs will be collected.

Adverse event information will be collected as shown in [Figure 3](#).

**Figure 3. Adverse Event Collection**

## 6.5 Adverse Event Reporting

In the event of a serious adverse event, whether associated with study drug or not, the Investigator will notify Clinical Pharmacovigilance within 24 hours of the site being made aware of the serious adverse event by entering the serious adverse event data into the electronic data capture (EDC) system. Serious adverse events that occur prior to the site having access to the RAVE® system or if RAVE is not operable s should use the SAE non-CRF paper forms and send them to Clinical Pharmacovigilance within 24 hours of the site being aware of the serious adverse event.

**FAX to:** [REDACTED]

**Email:** [REDACTED]

For safety concerns, contact the Antiviral Safety Team at:

For any subject safety concerns, please contact the Primary Study Designated Physician listed below:

In case of subject safety concerns or medical emergencies when the Primary Study Designated Physician is unavailable, please call the following central back-up number:

Phone: 
---

The sponsor will be responsible for Suspected Unexpected Serious Adverse Reactions (SUSAR) reporting for the Investigational Medicinal Product (IMP) in accordance with Directive 2001/20/EC. The reference document used for SUSAR reporting in the EU countries will be the most current version of the Investigator's Brochure.

## **6.6 Pregnancy**

Subjects and their partners should avoid pregnancy and males should avoid sperm donation throughout the course of the study, starting with Day 1 and for 7 months after the last dose of RBV (or per local RBV label) and/or consistent with local treatment guidelines for RBV.

Pregnancy in a study subject must be reported to AbbVie within 1 working day of the site becoming aware of the pregnancy. Subjects who report a positive pregnancy test during the Treatment Period must be notified to stop RBV immediately. Subjects will be monitored for SVR in the Post-Treatment Period as described in Section 5.1.3. Administration of DAAs may be continued at the investigator's discretion, if the benefit of continuing therapy is felt to outweigh the risk.

Information regarding a pregnancy occurrence in a study subject and the outcome of the pregnancy will be collected for pregnancies occurring up to 7 months (or per local RBV label) after the last dose of RBV for treatment with DAAs plus RBV. The investigator is encouraged to report the pregnancy information to the voluntary RBV Pregnancy Registry, if RBV is included within the regimen.

Subjects who discontinue study medications due to pregnancy will be monitored for SVR in the Post-Treatment Period as described in Section 5.1.3.

Pregnancy in a study subject is not considered an adverse event. However, the medical outcome of an elective or spontaneous abortion, stillbirth or congenital anomaly is considered a serious adverse event and must be reported to the Sponsor within 24 hours of the site becoming aware of the event.

## **6.7 Toxicity Management**

For the purpose of medical management, all adverse events and laboratory abnormalities that occur during the study must be evaluated by the Investigator. A table of Clinical Toxicity Grades for evaluating laboratory abnormalities is provided in [Appendix C](#). This table should be used in determination of the appropriate toxicity management as discussed in Section [6.7.1](#) and Section [6.7.5](#).

A drug-related toxicity is an adverse event or laboratory value outside of the reference range that is judged by the Investigator or the Sponsor as having a "reasonable possibility" of being related to the study drug (Section [6.3](#)). A toxicity is deemed "clinically significant" based on the medical judgment of the Investigator. Laboratory abnormalities will be managed as deemed clinically appropriate by the investigator until resolved.

Investigators should avoid interrupting study drugs for more than 7 consecutive days. The Investigator should ensure that any study drug interruptions or RBV dose modifications and associated adverse events are promptly entered into the appropriate eCRFs.

The toxicity management guidelines below should be followed throughout the Treatment Period of the study.

### **6.7.1 Grades 1 or 2 Laboratory Abnormalities and Mild or Moderate Adverse Events**

Subjects who develop a mild or moderate adverse event or Grade 1 or 2 laboratory abnormality, other than those discussed separately in Section [6.7.4](#) and Section [6.7.5](#), may continue study drugs with follow-up per study protocol and in accordance with local standard of care.

## **6.7.2                    Grades 3 or 4 Laboratory Abnormalities and Severe or Serious Adverse Events**

### **Grade 3 – 4 Laboratory Abnormalities**

With the exception of Grade 3 or higher abnormalities of total bilirubin, uric acid, phosphorus, total cholesterol, triglycerides, or glucose (in subjects with a history of diabetes), if a subject experiences a Grade 3 or greater abnormal laboratory parameter during the Treatment Period, the abnormal laboratory test should be repeated. If the Grade 3 or greater abnormality is confirmed, the investigator should assess whether the abnormality can be managed medically without interruption of study drug, or whether study drugs should be interrupted and the laboratory parameter followed until it improves. If study drugs are interrupted and restarted and the abnormality recurs, then study drugs should be permanently discontinued.

Decreases in serum hemoglobin or elevations of serum ALT should be managed according to the guidance in Section 6.7.4 and Section 6.7.5 below. Grade 3 or greater abnormalities of total bilirubin, uric acid, phosphorus, total cholesterol, triglycerides or glucose (in subjects with a history of diabetes) should be managed medically as appropriate and do not require confirmation or study drug interruption unless deemed necessary by the investigator.

### **Severe Adverse Event or Serious Adverse Events**

If a subject experiences a severe adverse event or a serious adverse event that the investigator considers to be a reasonable possibility of relationship to study drug, investigator should assess whether the adverse event can be managed medically without interruption of study drug, or whether study drugs should be interrupted until it improves, or study drugs should be permanently discontinued. If study drugs are interrupted and restarted and the adverse event recurs, then study drugs should be permanently discontinued.

If a subject experiences a severe adverse event or serious adverse event that is considered unrelated (no reasonable possibility) to the study drugs, it is not necessary to interrupt study drugs unless an interruption is required because of the nature of the event (e.g., unable to take oral medications). If an interruption is required, it should not exceed 7 days.

The investigator should ensure that all serious adverse events are reported to AbbVie within 24 hours of awareness. Serious adverse event follow-up information, including associated dose interruptions (or discontinuations), must be reported to AbbVie within 24 hours of awareness by entering updated SAE information into the appropriate eCRFs.

Severe adverse events and any associated dose interruptions (or discontinuations) should be entered into the appropriate eCRFs.

### **6.7.3 Management of Hemoglobin Decreases**

Reductions in hemoglobin are a well characterized side effect of ribavirin exposure. If a subject experiences a hemoglobin decrease meeting one of the criteria outlined in [Table 13](#), a confirmatory test should be performed. If the hemoglobin decrease is confirmed, the management guidelines in [Table 13](#) should be followed. Management will be different for subjects without a history of known cardiac disease and subjects with known cardiac disease.

Use of hematologic growth factors (such as erythropoietin or filgrastim) or blood transfusions are permitted at the discretion of the Investigator. Management of hematologic growth factor therapy is the responsibility of the Investigator, and growth factors will not be provided by AbbVie.

Alternate management of hemoglobin decreases outside of these criteria requires approval of the AbbVie Study Designated Physician.

**Table 13. Ribavirin Dose Modification Guidelines in Management of Hemoglobin Decreases**

Hemoglobin Value	Intervention
All subjects	
< 10 g/L and $\geq$ 8.5 g/dL for subjects without cardiac disease	Reduce RBV dose*. Study drugs may be continued. If hemoglobin increases to $\geq$ 10 g/dL for subjects without cardiac disease or to 12g/dL for subjects with cardiac disease. RBV dose may be increased gradually in 200 mg increments towards original dose.
< 12 g/L and $\geq$ 8.5 g/dL for subjects with cardiac disease	
< 8.5 g/dL	Interrupt ribavirin. Manage the subject as medically appropriate. Investigator should evaluate if RBV discontinuation is warranted. If subsequent hemoglobin results are improved to $\geq$ 10 g/dL for subjects without cardiac disease or 12 g/dL for subjects with cardiac disease RBV, may be restarted.
Additional guidance for subjects with history of stable cardiac disease	
Hemoglobin decrease of $\geq$ 2 g/dL during any 4-week treatment period	Reduce RBV dose*. If a subsequent hemoglobin result is greater than the level that triggered the dose reduction, RBV dose may be increased gradually in 200 mg increments
< 12 g/dL after a 4-week RBV dose reduction	Interrupt ribavirin. Manage the subject as medically appropriate. Investigator should evaluate if RBV discontinuation is warranted. If subsequent hemoglobin results are improved to $\geq$ 12g/dL, RBV may be restarted.

\* 1st dose reduction of ribavirin is to 600 mg/day. If needed, 2nd dose reduction of ribavirin is by an additional 200 mg/day. Subjects whose dose of ribavirin is reduced to 600 mg daily receive one 200 mg tablet in the morning and two 200 mg tablets in the evening.

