#### 6.7.4 Management of Transaminase Elevations

Transient asymptomatic Grades 3 – 4 ALT elevations have been observed in approximately 1% of subjects receiving ABT-450/r-containing regimens. If a subject experiences an increase in ALT to  $> 10 \times$  ULN, or to  $> 5 \times$  ULN which was increased from previous measurement, the subject should have a confirmatory ALT measurement performed in a timely fashion. If the ALT increase is confirmed, the management guidelines in [Table 14](#) should be followed. Subjects using an estrogen-containing product should discontinue use of that product. Alternate management of ALT increases is permitted with approval of the AbbVie Study Designated Physician.

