### 6.7.5 Management of eGFR Decreases

If calculated eGFR is confirmed to have decreased to  $< 50$  mL/minute, medical evaluation should include a full review of current medications, including those taken on an as needed basis, those which are sold over the counter and any dietary and herbal supplements, and appropriate dose reduction or discontinuation based on impaired renal function should be done (if applicable). Ribavirin dose should be adjusted as in [Table 15](#). Alternative management of RBV dose in the setting of reduced renal function will require approval of the AbbVie Study Designated Physician.

The investigator should also consider whether drug-drug interactions with concomitant medications may have contributed to the decrease in eGFR, and whether discontinuation of substitution of the possible interacting drug should be considered. For example, drug interactions between DAAs and some antihypertensive medications could potentially increase exposures of the antihypertensive and may reduce renal function. If anti-hypertensive medications are adjusted, vital signs must be monitored to ensure appropriate blood pressure control. Refer to Section 5.2.3.3 for additional information regarding drug-drug interactions.

If eGFR improves, the site should perform all necessary readjustment of any dose modifications that have been made.

The Investigator should ensure that any concomitant medication changes, RBV dose reductions, and study drug discontinuations, as well as consequent related adverse events are entered into the appropriate eCRFs.

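### Table 13 prints the upper limits of both general ribavirin dose-reduction bands in g/L, so no hemoglobin value can meet them, and Sections 6.7.1 and 6.7.2 do not point to the hemoglobin rules in 6.7.3

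*Protocol*

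**What the plan says.** Section 6.7.3 of the protocol ties both the confirmatory test and the ribavirin action to Table 13. It opens the rule with "If a subject experiences a hemoglobin decrease meeting one of the criteria outlined in" that table, and it requires approval from the sponsor's designated physician for any management outside those criteria.

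Under the heading for all subjects, Table 13 gives two bands in which ribavirin is to be reduced:

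- "< 10 g/L and $\geq$ 8.5 g/dL for subjects without cardiac disease"
- "< 12 g/L and $\geq$ 8.5 g/dL for subjects with cardiac disease"

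The intervention cell of the same row sets the level at which the dose may be raised again: "If hemoglobin increases to $\geq$ 10 g/dL for subjects without cardiac disease or to 12g/dL for subjects with cardiac disease". The next row interrupts ribavirin below 8.5 g/dL. Two further rows cover stable cardiac disease.

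Two other sections direct the reader according to grade. Section 6.7.2 (Grade 3 or 4) states: "Decreases in serum hemoglobin or elevations of serum ALT should be managed according to the guidance in Section 6.7.4 and Section 6.7.5 below". Those sections are headed "6.7.4 Management of Transaminase Elevations" and "6.7.5 Management of eGFR Decreases". Section 6.7.1 (Grade 1 or 2) lets subjects stay on study drugs, and the only exceptions it names are the abnormalities covered in 6.7.4 and 6.7.5.

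**The concern.** Each reduction band has its upper limit in g/L and its lower limit in g/dL. Taken literally, the upper limit lies far below the lower one, so the band contains nothing. A subject without cardiac disease at 9 g/dL would then meet no Table 13 criterion. The confirmatory test would not be triggered, and the intended ribavirin reduction would count as management outside the criteria.

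The pointers add to this. A reader who starts from the grade-based sections is never sent to 6.7.3: one section directs hemoglobin events to the wrong places and the other leaves hemoglobin out of its exceptions. Section 6.7.3 itself describes hemoglobin reduction as a well-known effect of ribavirin, so these limits will be used in practice and should be right on the page.

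**Working it through.** **1. Unit check.** Appendix C (hemoglobin, Grade 2) equates 10.0 g/dL with 100 g/L, so 1 g/dL = 10 g/L.

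| Band | Upper limit as printed | Upper limit in g/dL | Lower limit | Values in band |
|---|---|---|---|---|
| No cardiac disease | 10 g/L | 10 / 10 = 1.0 | 8.5 g/dL | none (1.0 < 8.5) |
| Cardiac disease | 12 g/L | 12 / 10 = 1.2 | 8.5 g/dL | none (1.2 < 8.5) |

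With g/dL throughout, the bands become 8.5 to < 10 g/dL (width 1.5) and 8.5 to < 12 g/dL (width 3.5). They then join the interruption row below 8.5 g/dL and the recovery thresholds of 10 and 12 g/dL without a gap.

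**2. Cross-references against headings.**

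| Section | Sections it names | What those sections cover | What it should name |
|---|---|---|---|
| 6.7.2, for hemoglobin and ALT | 6.7.4, 6.7.5 | transaminases, eGFR | 6.7.3, 6.7.4 |
| 6.7.1, exceptions | 6.7.4, 6.7.5 | transaminases, eGFR | 6.7.3, 6.7.4, 6.7.5 |

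Appendix C puts Grade 2 hemoglobin at 8.0 to < 10.0 g/dL. Between 8.0 and < 8.5 g/dL, Section 6.7.1 therefore permits continuation while Table 13 calls for ribavirin to be interrupted. The specific rule would govern, so this is a missing exception and not a true conflict.

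**3. How many subjects the hemoglobin rules concern.** The protocol states no such figure for this trial. Table 3 gives rates for the earlier 12-week cirrhotic arm, N = 208.

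- Below 10 g/dL: 7.2%. Only 15/208 = 7.21% rounds to this (14/208 = 6.73%, 16/208 = 7.69%).
- Below 8.0 g/dL: 1.4%. Only 3/208 = 1.44% rounds to this (2/208 = 0.96%, 4/208 = 1.92%).
- Worst value 8.0 to < 10 g/dL: 15 − 3 = 12, and 12/208 = 5.77%. This assumes that the first row includes the second, as the Section 3.0 text on reductions of Grade 2 or higher indicates.

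Wilson 95% interval, with z = 1.96:

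[p + z²/(2n) ± z·√(p(1−p)/n + z²/(4n²))] / (1 + z²/n)

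For 15/208: (0.07212 + 0.00924 ± 0.03635) / 1.01847, which gives 4.42% to 11.56%.

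| Hemoglobin | x/208 | Rate | 95% CI | Per 100 subjects |
|---|---|---|---|---|
| < 10 g/dL | 15 | 7.21% | 4.42% to 11.56% | about 7 (4 to 12) |
| < 8.0 g/dL | 3 | 1.44% | 0.49% to 4.15% | about 1 (0 to 4) |
| 8.0 to < 10 g/dL | 12 | 5.77% | 3.33% to 9.81% | about 6 (3 to 10) |

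The last line includes values from 8.0 to < 8.5 g/dL, where Table 13 is correct. The protocol gives no split at 8.5 g/dL and no rate below 12 g/dL for subjects with cardiac disease.

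**The case against.** The strongest reply is that this is an editorial slip with no demonstrable effect. The row settles its own unit: the lower limit is 8.5 g/dL, the recovery thresholds are in g/dL, and no clinician would act on a limit of 1.0 g/dL. For subjects with cardiac disease a correctly printed reduction trigger remains, a fall of at least 2 g/dL within any 4 weeks of treatment, which would catch many though not all of those in the second band. Section 6.7.3 applies by its own wording and needs no pointer, it directly follows 6.7.2, and Section 6.7 asks sites to follow all the guidance beneath it. Section 6.7.1 is permissive and refers back to the protocol. At 8.5 to < 10 g/dL it agrees with Table 13, which also lets study drugs continue. Finally, the earlier trial's hemoglobin rates do not measure what the misprint does.

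Most of this stands, and it is why the point is minor. It shows that the consequence is small; it does not make the printed limits or pointers correct. The rates above give scale only. An error in reading the PDF cannot be wholly excluded, but it is unlikely: g/L appears in both band cells and nowhere else in the table, beside a lower limit in g/dL.

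**Conclusion.** Wrong as written, and minor. Both general dose-reduction bands in Table 13 are empty as printed, and neither grade-based section points to 6.7.3. The intended rule is not in dispute, and the interruption row below 8.5 g/dL and both stable-cardiac rows are correct.

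If the earlier cirrhotic rates carry over to this Asian population, the hemoglobin rules would concern about 7 in 100 subjects (4 to 12) below 10 g/dL. About 1 in 100 (0 to 4) would fall below 8.0 g/dL, the Grade 3 group that Section 6.7.2 misdirects. These are estimates and not upper limits, and the protocol supports no figure for misdosed subjects. Sample size, power and the primary analysis are untouched. The reason to correct it is that Section 6.7.3 makes these limits the trigger for action, and a dosing threshold should not depend on each site inferring the unit.

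**What to change.** - **Table 13:** change the two upper limits to g/dL, so that the bands read < 10 g/dL and ≥ 8.5 g/dL without cardiac disease, and < 12 g/dL and ≥ 8.5 g/dL with cardiac disease.
- **Section 6.7.2:** cite 6.7.3 for hemoglobin and 6.7.4 for ALT.
- **Section 6.7.1:** add 6.7.3 to the listed exceptions.

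The cost is two unit corrections and two cross-reference corrections. No intended dosing rule changes, and nothing changes in the sample size, the primary analysis or the visit schedule.
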